10.2. Sample Size Determination

In Part 1, 80 participants in Cohorts 1-4 will be randomly assigned study intervention (CAB 400 mg/mL or AC CAB 200 mg/mL), 24 participants in Cohort 4b will receive study intervention with CAB 400 mg/mL, and approximately 20 participants in Cohort 4h will be randomly assigned study intervention rHuPH20 with CAB 400 mg/mL or CAB 200 mg/mL, such that approximately 93 evaluable participants will be receiving CAB (15 in each of Cohorts 1-4 and Cohort 4h, 18 in Cohort 4b). In Part 2, 22-44 participants will be enrolled to Cohort 5 and 6 (if conducted) and randomly assigned study intervention (CAB 400 mg/mL or AC CAB 200 mg/mL) such that approximately 16 evaluable participants receiving CAB from each cohort complete the study.

With the determined sample size, certain statistical precision can be achieved when estimating PK trough concentrations using sample geometric mean trough concentration as shown below in [Table 3](#):

Table 3 Statistical Precision When Estimating PK Trough Concentration

Exp. Arm	Time Point	Assumptions*			Precision+ when estimating trough Concentration 90%CI	
		Mean (LgConc.)	SD (LgConc.)	True Geo. Mean (To be observed)		
Cohorts 1-4: 600 mg - >400 mg Q4W (N=15)	Week 4	0.3291	0.66079	1.3898	1.0290	1.8769
	Week 8	0.6123	0.47376	1.8446	1.4871	2.2881
Cohort 4h: 400 mg Q4W (N=8)	Week 4	0.3292	0.66079	1.3898	0.8927	2.1636
Cohorts 5/6: 1200 mg Q3M (N=16)	Week 12	0.0311	0.59603	1.0316	0.7944	1.3395
	Week 24	-1.3837	1.11507	0.2507	0.1538	0.4086

*Assumptions for Q4W arm were from pooled PK Trough data from FLAIR (Study 201584) and ATLAS (Study 201585) i.e. 1.44 µg /mL; assumptions for Q3M were from simulated PK Trough data from a single 1200 mg dose in 80% male and 20% female.

+Precisions were calculated based on t-distribution.

In addition, the bioavailability of CAB 400 mg/mL formulation administered IM to *gluteus medius* will be assessed relative to IM administration to lateral thigh or SC administration to abdomen from Q4W cohorts of Part 1. Additionally, C_τ following

CAB 400 mg/mL formulation administration in Part 1 will be compared to historical PK data of CAB 200 mg/mL using cross-study comparisons.

Table 4 Statistical Precision When Estimating Ratio of PK Trough Concentration

Exp. Arm	Time Point	Assumptions*			Precision* for estimating Ratio of Trough Concentration		
		CVb%	SD (LgConc.)	Ratio of Geo. Mean Concentration (To be observed)	Half Width of (Δ Lg Conc).	90% CI for Ratio	

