Cohorts 1-4: CAB 400 mg/ml (N=15)/ Historical CAB 200 mg/ml (N=579)	Week 4	74%	0.66079	0.7	0.28470	0.5266	0.9306
				0.8		0.6018	1.0635
				0.9		0.6770	1.1964
				1.0		0.7522	1.3294
				1.1		0.8275	1.4623
				1.2		0.9027	1.5952
				1.3		0.9779	1.7282
Cohort 4h: CAB 400 mg (N=8)/ Historical CAB 200 mg/ml (N=579)	Week 4	74%	0.66079	0.7	0.387538	0.4751	1.0313
				0.8		0.5430	1.1787
				0.9		0.6109	1.326
				1.0		0.6787	1.4733
				1.1		0.7466	1.6207
				1.2		0.8145	1.768
				1.3		0.8823	1.9154
Cohorts 1-4: CAB 400 mg/ml (N=15) / Historical CAB 200 mg/ml (N=577)	Week 8	50%	0.47376	0.7	0.20413	0.5707	0.8585
				0.8		0.6523	0.9812
				0.9		0.7338	1.1038
				1.0		0.8154	1.2265
				1.1		0.8969	1.3491
				1.2		0.9784	1.4717
				1.3		1.0600	1.5944

* CVb%, SD (Lg Conc) is from pooled Cabotegravir trough concentration data from ATLAS and FLAIR studies

+Precisions were calculated based on t-distribution.

CCI

CCI

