10.4.2. Primary Endpoints

The primary endpoints are injection phase PK parameters including C_{max}, t_{max}, C_τ, AUC_{0-t}, terminal phase half-life(t_{1/2}) and absorption rate constant (K_A) for each cohort. The PK Parameter Population will be used for the analyses of these endpoints.

Following log_e-transformation, the PK parameters will be summarized by treatment and time period if applicable. Summary statistics (such as mean, standard deviation, median, min, max) will be produced for the log_e-transformed PK parameters. The Summary statistics will also be back-transformed to the original scale to produce geometric mean and between participant coefficient variation (CV_b).

In addition, the primary analyses will also include the following assessments based on geometric mean ratios:

- Pair-wise comparisons between Cohorts 1, 2, 3, 4, 4b, and 4h for CAB 400 mg/mL plasma trough concentrations (C_τ), C_{max} and AUC_{0-t} at Week 4 (Injection 1 Day 28) and Week 8 (Injection 2 Day 28) where administered via different routes;
- CAB 200 mg/mL plasma trough concentrations (C_τ) at Week 4 (Injection 1 Day 28) for Cohorts 4h compared to historical CAB 200 mg/mL data (Week 8 C_τ following first injection at Week 4b in ATLAS/FLAIR);
- CAB 400 mg/mL plasma trough concentrations (C_τ) at Week 4 (Injection 1 Day 28) for Cohorts 1, 2, 3, 4, 4b and 4h compared to historical CAB 200 mg/mL data (Week 8 C_τ following first injection at Week 4b in ATLAS/FLAIR);
- CAB 400 mg/mL plasma trough concentrations (C_τ) at Week 8 (Injection 2 Day 28) for Cohorts 1, 2, 3, 4, and 4b compared to historical CAB 200 mg/mL data (Week 12 C_τ following second injection at Week 8 in ATLAS/FLAIR);
- CAB 400 mg/mL plasma trough concentrations (C_τ) at Week 12 (Injection 1 Week 12) for Cohorts 5 and 6 (if conducted) compared to historical CAB 200 mg/mL data (Week 8 C_τ following first injection at Week 4b in ATLAS/FLAIR).

Relative bioavailability assessments using pair-wise comparisons between cohorts in the current study may be done with dose-normalized PK parameters if the doses administered are different in different cohorts.

Following log transformation, PK concentration or PK parameters will be separately analyzed using a linear regression model with fixed effect terms for the treatment. Point estimates and corresponding 90% confidence intervals will be constructed for the differences (CAB 400 mg/mL – CAB 200 mg/mL). The point estimates and their 90%

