2. SUMMARY OF KEY PROTOCOL INFORMATION

2.1. Changes to the Protocol Defined Statistical Analysis Plan

There were no changes or deviations to the originally planned statistical analysis specified through protocol amendment 6.

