8.1.5.1. Statistical Methodology Specification

The following PK statistical analyses will only be performed if sufficient data is available (i.e., if participants have well defined plasma profiles).

Endpoint / Variables

 AUC(0-τ), C_{max}, and C_{τ} for CAB 400 mg/mL following CAB IM (gluteus medius or vastus lateralis) or SC dosing
Model Specification for Pairwise and Historical Comparisons

 Pairwise comparisons between cohorts receiving the same dose of CAB400 but via different administration routes of CAB 400 mg/mL geometric mean plasma C_{τ}, C_{max}, and plasma AUC(0-τ) for Cohorts 1, 2, 3, 4, 4b and 4h will be conducted, as specified in Section 5.1. Cross study comparisons of geometric mean plasma C_{τ} for Cohorts 1, 2, 3, 4, 4b and 4h, and Cohort 5 compared to historical CAB 200 mg/mL data will be conducted, as specified in Section 5.1. Following log transformation, PK parameters will be separately analyzed using a linear regression model with a fixed effect term for treatment, with allowance for unequal variances for each treatment group (using the repeated / group=treatment option in the MIXED procedure to model unequal variances and DDFM=KENWARDROGER option for adjusted degrees of freedom). Point estimates and corresponding 90% CIs will be constructed for the treatment differences. Point estimates and their 90% CIs will then be transformed back to provide point estimates and 90% CIs on the original scale.
Historical CAB 200 mg/mL Data

 Anonymized reference dataset(s) containing the historical PK data from the ATLAS [201585], FLAIR [201584], and ÉCLAIR [201120] studies will be used in the historical cross-study comparison analyses described above. For ATLAS and FLAIR, concentrations meeting the definition of 'evaluable' as defined in the study-specific RAPs (e.g., excluding samples collected outside the ± 4 days evaluable sample window) will be used.
Model Checking & Diagnostics

 Model assumptions will be applied, but appropriate adjustments may be made based on the data.
Model Results Presentation

 Statistical analysis by analysis of variance (ANOVA) will be presented in tabular format with geometric mean ratios and corresponding 90% CI for the comparisons mentioned above.

Endpoint / Variables

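### Protocol Table 4 states its 90% CIs for the historical trough ratios on a common variance, while the SAP analyses those ratios with separate variances, so the table overstates precision, most of all for Cohort 4h

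*Protocol*

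**What the plan says.** Protocol 10.2 justifies the sample size by precision. Table 4 covers ratios of trough concentration to historical CAB 200 mg/mL data in three blocks: "Cohorts 1-4: CAB 400 mg/ml (N=15)/ Historical CAB 200 mg/ml (N=579") at Week 4, "Cohort 4h: CAB 400 mg (N=8)/ Historical CAB 200 mg/ml (N=579") at Week 4, and "Cohorts 1-4: CAB 400 mg/ml (N=15) / Historical CAB 200 mg/ml (N=577") at Week 8. Each block has one SD on the log scale, and the footnote gives its source: "CVb%, SD (Lg Conc) is from pooled Cabotegravir trough concentration data from ATLAS and FLAIR studies". The table says its precision rests on the t-distribution but gives no degrees of freedom.

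Protocol 10.4.2 specifies, after log transformation, a linear regression with a treatment effect, and says that "corresponding 90% confidence intervals will be constructed for the differences". It does not say whether the groups share a variance. SAP 8.1.5.1 does say: the historical and pairwise comparisons are fitted "using the repeated / group=treatment option in the MIXED procedure to model unequal variances and DDFM=KENWARDROGER option for adjusted degrees of freedom". SAP 2.1 states: "There were no changes or deviations to the originally planned statistical analysis specified through protocol amendment 6".

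Protocol 10.2 also gives the evaluable numbers behind its total of 93: "15 in each of Cohorts 1-4 and Cohort 4h, 18 in Cohort 4b". Cohort 4h is randomized 1:1 to two CAB formulations, and Tables 3 and 4 take N=8 for it.

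**The concern.** Geometric mean ratios of trough concentration against historical data are a primary endpoint. No hypothesis is tested, so precision is the study's sample-size argument, and Table 4 is the only place that states it for these ratios.

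The two error terms differ greatly when 8 or 15 participants are set against 577 to 579. Under a common variance, the historical group supplies nearly all the information on the SD and the t quantile is close to normal. Under separate variances, the small cohort must estimate its own SD and the degrees of freedom fall to roughly its own N minus 1. The reported CI will therefore tend to be wider than a reader of Table 4 expects.

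The protocol's own tables give a visible sign of this. Table 3, which uses the cohort's own degrees of freedom, implies a log half-width of 0.443 for the Cohort 4h mean alone. Table 4 gives 0.388 for the ratio of that same mean to a second estimated mean. A ratio of two independent estimates appears more precise than one of its components only because of the degrees of freedom taken from the historical data.

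**Working it through.** **Inputs.** From Table 4: N = 15 vs 579, 8 vs 579 and 15 vs 577; SD of log concentration 0.66079 (Week 4) and 0.47376 (Week 8), the same in both groups. The two-sided 90% CI comes from Protocol 10.4.2, so the 0.95 quantile of t applies.

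**Formula.** Half-width h = t(0.95, df) × SD × √(1/n1 + 1/n2). CI = ratio × exp(±h).

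**Step 1: reproduce Table 4.** Take df = n1 + n2 − 2.

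| Block | SE | df | t | h | Table 4 |
|---|---|---|---|---|---|
| Cohorts 1-4, Week 4 | 0.17281 | 592 | 1.6474 | 0.28469 | 0.28470 |
| Cohort 4h, Week 4 | 0.23523 | 585 | 1.6475 | 0.38754 | 0.387538 |
| Cohorts 1-4, Week 8 | 0.12390 | 590 | 1.6474 | 0.20412 | 0.20413 |

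The tabulated CIs agree to within 0.0001. A normal quantile (0.28425, 0.38692, 0.20380) and df = n1 − 1 (0.30437, 0.44567, 0.21823) do not reproduce the table, so it uses a common variance.

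**Step 2: the same inputs under the SAP model.** With two independent groups and separate variances, Satterthwaite df stand in for Kenward-Roger: df = (v1 + v2)² / [v1²/(n1 − 1) + v2²/(n2 − 1)], with vi = SD²/ni. For Cohort 4h, v1 = 0.66079²/8 = 0.05458 and v2 = 0.66079²/579 = 0.00075, so df = 7.2. The SE is unchanged; only the quantile moves.

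| Block | df | t | h | Change in h | CI at ratio 1.0 | Table 4 CI |
|---|---|---|---|---|---|---|
| Cohorts 1-4, Week 4 | 14.7 | 1.7551 | 0.3033 | +6.5% | 0.738 to 1.354 | 0.7522 to 1.3294 |
| Cohort 4h, Week 4 | 7.2 | 1.8869 | 0.4439 | +14.5% | 0.642 to 1.559 | 0.6787 to 1.4733 |
| Cohorts 1-4, Week 8 | 14.7 | 1.7551 | 0.2175 | +6.5% | 0.805 to 1.243 | 0.8154 to 1.2265 |

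For Cohort 4h at ratio 0.8 the CI moves from (0.543, 1.179) to (0.513, 1.247), and at 1.3 from (0.882, 1.915) to (0.834, 2.026).

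**Step 3: allow for the SD being estimated.** Step 2 inserts the true SD, as Table 4 does. When both variances are simulated with equal true SDs, the mean SAP-model half-widths are 0.298, 0.428 and 0.214. Against Table 4 that is 0.298/0.28470 = 1.05, 0.428/0.387538 = 1.10 and 0.214/0.20413 = 1.05. The medians at Week 4 are 0.296 (N=15) and 0.422 (N=8). At N=8, 80% of SAP-model half-widths fall between 0.28 and 0.58, against 0.37 to 0.40 under a common variance.

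**Step 4: compare with Table 3.** Its intervals imply ln(2.1636/1.3898) = 0.443 for Cohort 4h, ln(1.8769/1.3898) = 0.300 for Cohorts 1-4 at Week 4 and ln(2.2881/1.8446) = 0.215 at Week 8. All three exceed the matching Table 4 ratio half-widths and sit just below those of Step 2.

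**Step 5: the 4h evaluable count.** 4 × 15 + 15 + 18 = 93, so the total counts 15 evaluable in Cohort 4h. Over two arms that is at most 8 and 7. At n1 = 7: SE = 0.25126, df = 6.1, t = 1.9349, h = 0.486.

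**The case against.** Four points can fairly be made against this.

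- **Table 4 is not miscalculated.** A reader might infer an arithmetic error. The documents do not support that: the table is right for a common-variance model, and Protocol 10.4.2 can be read as that model. This stands in full. The fault is the mismatch with the SAP.
- **SAP 2.1 may not be false.** A reader might infer an undeclared departure from the protocol. Protocol 10.4 describes itself as a summary, leaves technical detail to the analysis plan, and nowhere states equal variances. Adding a variance structure and a degrees-of-freedom method can be read as that delegated detail. What remains is that nobody comparing Table 4 with the results is told that the error term differs.
- **Table 3 already shows the small-cohort width.** It does, for single means, so the wide 4h interval is not hidden. But Table 3 does not present those as ratio CIs, and it leaves the ratio CIs in Table 4 as they are.
- **The plug-in percentages are the larger version.** This stands too: expected widening is about 5% and 10%. The plug-in figures are still the right replacements for a table built on a plug-in basis.

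On the evaluable count, a reader might infer that the 4h target cannot supply N=8 at all. It can in one arm, the wording is approximate, and replacement of participants who discontinue is allowed. The mismatch is one participant.

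**Conclusion.** The point holds as a mismatch between the stated precision and the planned analysis. Table 4 overstates the precision of the historical ratios by a modest amount at N=15 (log half-width +6.5% plug-in, about 5% on average) and a more noticeable one for Cohort 4h (+14.5% plug-in, about 10% on average).

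This rests on Table 4's assumption that the study cohorts share the ATLAS/FLAIR SD, and on Satterthwaite df in place of Kenward-Roger. A different SD in a study cohort would move the width further, in either direction.

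A reader might also infer that the reported intervals will be too narrow or invalid. They will not: they come from the SAP model, which is the safer choice because it does not assume that a small cohort has the Phase 3 variance. No hypothesis, power or success criterion depends on Table 4.

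**What to change.** 1. Keep the SAP 8.1.5.1 model.
2. Restate Table 4, in the protocol or the SAP, with half-widths 0.303 (Cohorts 1-4, Week 4), 0.444 (Cohort 4h, Week 4) and 0.217 (Cohorts 1-4, Week 8), and recompute the CI at each tabulated ratio as ratio × exp(±h).
3. Add a sentence to the SAP, most naturally in 2.1, saying that the historical comparisons use separate variances per group and that this differs from the common-variance basis of Table 4 in the protocol.
4. As a minor point, align the 4h evaluable target with the tables. Either state 8 per arm, giving 16 in Cohort 4h and a total of 93 + 1 = 94, or show the N=7 half-width of 0.486 alongside the N=8 row.

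The cost is a table restatement and a sentence or two, with slightly less favourable stated figures. It adds no enrolment: 16 evaluable lies within the 20 participants already planned for Cohort 4h.

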10.3. Populations for Analyses

The following populations are defined:

Population	Description
Screened	All participants who were screened for eligibility.
Enrolled	All participants who passed screening and entered the study. Note: screening failures (who never passed screening even if rescreened) and participants screened but never enrolled into the study are excluded from the Enrolled population as they did not enter the study.
Randomized	All participants who were randomly assigned to treatment in the study.
Safety Population	All participants who received at least one dose of study treatment (oral or injection). This population will be based on the treatment the participant received. The Safety population will be used for Safety analyses and summarization of baseline/demographic characteristics.
Pharmacokinetic	All participants in the Safety population who received study treatment and had at least 1 non-missing PK assessment (non-quantifiable [NQ] values will be considered as non-missing values). Note: PK samples that may be affected by protocol deviations will be reviewed by the study team to determine whether or not the sample will be excluded.

10.4. Statistical Analyses

This section is a summary of the planned statistical analyses of the most important endpoints including primary and key secondary endpoints. Further technical details of the planned statistical analyses will be provided in the reporting and analysis plan (RAP). PopPK model-based simulations on proportions of participants achieving the clinical target will be described in a separate CPMS RAP.

10.4.1. General Considerations

Pharmacokinetic analysis that involves PK modelling to produce the PK parameters will be the responsibility of the Clinical Pharmacology Modelling & Simulation department within GlaxoSmithKline. Statistical analyses of the pharmacokinetic concentration and pharmacokinetic parameters and all other clinical data including safety and demographic data will be the responsibility of Clinical Statistics & Programming, GlaxoSmithKline.

10.4.2. Primary Endpoints

The primary endpoints are injection phase PK parameters including C_{max}, t_{max}, C_τ, AUC_{0-t}, terminal phase half-life(t_{1/2}) and absorption rate constant (K_A) for each cohort. The PK Parameter Population will be used for the analyses of these endpoints.

Following log_e-transformation, the PK parameters will be summarized by treatment and time period if applicable. Summary statistics (such as mean, standard deviation, median, min, max) will be produced for the log_e-transformed PK parameters. The Summary statistics will also be back-transformed to the original scale to produce geometric mean and between participant coefficient variation (CV_b).

In addition, the primary analyses will also include the following assessments based on geometric mean ratios:

- Pair-wise comparisons between Cohorts 1, 2, 3, 4, 4b, and 4h for CAB 400 mg/mL plasma trough concentrations (C_τ), C_{max} and AUC_{0-t} at Week 4 (Injection 1 Day 28) and Week 8 (Injection 2 Day 28) where administered via different routes;
- CAB 200 mg/mL plasma trough concentrations (C_τ) at Week 4 (Injection 1 Day 28) for Cohorts 4h compared to historical CAB 200 mg/mL data (Week 8 C_τ following first injection at Week 4b in ATLAS/FLAIR);
- CAB 400 mg/mL plasma trough concentrations (C_τ) at Week 4 (Injection 1 Day 28) for Cohorts 1, 2, 3, 4, 4b and 4h compared to historical CAB 200 mg/mL data (Week 8 C_τ following first injection at Week 4b in ATLAS/FLAIR);
- CAB 400 mg/mL plasma trough concentrations (C_τ) at Week 8 (Injection 2 Day 28) for Cohorts 1, 2, 3, 4, and 4b compared to historical CAB 200 mg/mL data (Week 12 C_τ following second injection at Week 8 in ATLAS/FLAIR);
- CAB 400 mg/mL plasma trough concentrations (C_τ) at Week 12 (Injection 1 Week 12) for Cohorts 5 and 6 (if conducted) compared to historical CAB 200 mg/mL data (Week 8 C_τ following first injection at Week 4b in ATLAS/FLAIR).

Relative bioavailability assessments using pair-wise comparisons between cohorts in the current study may be done with dose-normalized PK parameters if the doses administered are different in different cohorts.

Following log transformation, PK concentration or PK parameters will be separately analyzed using a linear regression model with fixed effect terms for the treatment. Point estimates and corresponding 90% confidence intervals will be constructed for the differences (CAB 400 mg/mL – CAB 200 mg/mL). The point estimates and their 90%

confidence intervals will then be transferred back to provide point estimates and 90% confidence intervals on the original scale.

10.4.3. Safety Endpoints

The safety endpoints are safety and tolerability parameters including adverse events, clinical laboratory tests, vital sign assessments. Liver biochemistry abnormalities are included as secondary endpoints. The Safety Population will be used for the analyses of the safety endpoints. Participants on active control CAB 200 mg/mL will also be combined as a single group for the analysis. Safety data will be presented in tabular and/or graphical format and summarized with descriptive statistics according to GSK's Integrated Data Standards Library (IDSL) standards.

10.4.4. Secondary Endpoints

The secondary endpoints are tolerability parameters including patient reported outcome measures and liver biochemistry abnormalities. Participants on active control CAB 200 mg/mL will also be combined as a single group for the analysis. The Safety Population will be used for the analyses for these endpoints. The secondary endpoints data will be presented in tabular and/or graphical format and summarized with descriptive statistics according to GSK's IDSL standards.

The secondary endpoints for the PK parameters following oral administration (i.e., AUC_{0-t}, C_{max}, t_{max}, Day 1 C₂₄, and C_τ) will be presented in tabular and/or graphical format and summarized with descriptive statistics according to GSK's IDSL standards.

10.4.5. Exploratory Endpoints for Cohort 4b and Other Cohorts

CCI

10.4.6. Bayesian Predictive Probability for Cohort 5 and 6 Dose Selection

A Bayesian predicted probability $\leq 50\%$ that any participant's C_{max} will exceed a criteria of 22.5 µg/mL following dose escalation is used to support dose selection for Cohort 5 and 6. See Section 4.2 for additional considerations for the determination of the dose and dosing schedule, and Section 4.2.3 for rationale supporting the C_{max} criteria of 22.5 µg/mL.

Cmax for Cohort 5 Injection 1 will be extrapolated from observed concentrations in Cohort 1 under the assumption of dose proportionality, using the following Bayesian model (with non-informative prior distributions for the model parameters):

$$y_i = \theta_1 + d_i + \varepsilon_{ij} \quad [1]$$

Where y_{ij} is the logarithm of Cmax for i -th participant; d_i is the logarithm of the dose received by the i -th participant, $\hat{\theta}_1$ is the population intercept, ε_i is random error of i -th participant (assumed to be normally distributed with mean 0).

Cmax for Injection 2 in Cohort 5 will be extrapolated from observed values in Cohort 1 following each injection and in Cohort 5 following injection 1 (for at least 50% of participants completing Week 4 assessments), using the following Bayesian mixed effects model [Whitehead, 2001] (with non-informative prior distributions for the model parameters):

$$y_{ij} = \theta_1 + \theta_2 d_{ij} + s_i + \varepsilon_{ij} \quad [2]$$

where y_{ij} is the logarithm of Cmax for the j -th observation on the i -th participant; d_{ij} is the logarithm of the j -th dose received by the i -th participant. $\hat{\theta}_1$ and $\hat{\theta}_2$ are the population intercept and slope, respectively, and s_i is the random effect of i -th participant and ε_{ij} is random error of i -th participant in j -th dose (assumed to be mutually independent, normally distributed random variables with mean 0). A similar modelling approach will be used for Cohort 6, if conducted.

Based on the above models, the Bayesian predictive probability for injection 1 and injection 2, respectively, following dose escalation is calculated according to the following MCMC procedure:

- For each iteration, obtain a random sample of model parameter values from the posterior parameter distribution estimated from the Bayesian model above:
 - $\hat{\theta}_1, \hat{\sigma}$ (the estimated standard deviation of ε_i) for model [1], or
 - $\hat{\theta}_1, \hat{\theta}_2, \hat{s}_i$ ($i, 2, \dots, 28$), $\hat{\sigma}$ (the estimated standard deviation of ε_{ij}) for model [2]
- For each of $n=20$ new participants, obtain a random sample for the predicted Cmax values corresponding to log-dose d from the following Normal distribution (mean, variance):
 - $N(\hat{\theta}_1 + d, \hat{\sigma}^2)$ for model [1], or
 - $N(\hat{\theta}_1 + \hat{\theta}_2 * d + \hat{s}_i, \hat{\sigma}^2)$ for model [2]
- Repeat steps 1 and 2 for 100,000 iterations;
- Count the number of iterations N in which any of the predicted Cmax values exceed the criteria of log (22.5);
- The Bayesian predictive probability is calculated as $\frac{N}{100000}$.

The selected Cohort 5 Injection 1 dose of 800 mg had a calculated Bayesian predicted value of 3.9%, which met the $\leq 50\%$ criterion for dose escalation. The same approach will be applied to Cohort 6 if conducted.

